6.3. Continuation of Treatment

Participants who complete the treatment and study through Day 91 will not receive any further treatment with the study drug on this study. Participants who complete the study, and meet eligibility requirements, will be provided with the opportunity to receive open-label inclacumab in the OLE study. The first dose administered in the OLE study will occur after completion of the end-of-study evaluations at the Day 91 visit.

ASSESSMENT OF SAFETY

Safety assessments will consist of AE and SAE monitoring, protocol-specified hematology, serum chemistry, and coagulation tests, physical examinations, protocol-specified vital sign measurements, and the results from other protocol-specified tests that are deemed critical to the safety evaluation of inclacumab.

The determination, evaluation, reporting, and follow-up of AEs will be performed as outlined in this section. At each visit/phone contact, the study participant or participant caregiver will be asked about any new or ongoing AE since the previous visit. Assessments of AEs will occur at each study visit and during monthly phone calls. See Section 7.2 for details regarding the required time periods for AE reporting.

Clinically significant changes from study Baseline in physical examination findings, weight, vital signs, and clinical laboratory test results will be recorded as AEs or SAEs, as appropriate.

7.1. Adverse Events

7.1.1. Definition of Adverse Events

An AE is defined as any untoward medical occurrence in a participant administered a pharmaceutical product during the course of a clinical investigation. An AE can therefore be any unfavorable and unintended sign, symptom, or disease temporally associated with the use of an investigational product, whether or not thought to be related to the investigational product. In addition to new events, any increase in the severity or frequency of a pre-existing condition that occurs after the participant signs the ICF for participation is considered an AE. This includes any side effect, injury, toxicity or sensitivity reaction.

A suspected adverse reaction is any AE for which there is a reasonable possibility that the drug caused the AE. For the purposes of expedited safety reporting, "reasonable possibility" means there is evidence to suggest a causal relationship between the drug and the AE. Suspected adverse reaction implies a lesser degree of certainty about causality than adverse reaction, which means any AE caused by a drug.

Life-threatening AE or life-threatening suspected adverse reaction is an AE or suspected adverse reaction that, in the view of either the Investigator or Sponsor, places the study participant at immediate risk of death. It does not include an AE or suspected adverse reaction that, had it occurred in a more severe form, might have caused death.

An AE or suspected adverse reaction is considered to be "unexpected" if it is not listed in the Reference Safety Information (RSI) section of the current IB or is not listed at the specificity or severity that has been observed.

7.1.2. Definition of Serious Adverse Events

An SAE or serious suspected adverse reaction is an AE or suspected adverse reaction that, at any dose, in the view of the either the Investigator or Sponsor, results in any of the following outcomes:

- Death
- A life-threatening AE

- Inpatient hospitalization or prolongation of existing hospitalization
- Persistent or significant incapacity or disability (substantial disruption of the ability to conduct normal life functions)
- A congenital anomaly/birth defect
- Important medical events that may not result in death, be immediately lifethreatening, or require hospitalization may be considered serious when, based upon medical judgment, they may jeopardize the study participant and may require medical or surgical intervention to prevent one of the outcomes listed in this definition.

NOTE: Hospitalization planned prior to study enrollment (eg, for elective surgeries) is not considered to be an SAE. Any complications arising from a planned hospitalization may be considered an adverse event and should be reported as applicable. Hospitalizations that occur for pre-existing conditions that are scheduled after study enrollment are considered SAEs.

The Investigator will assess each AE for seriousness, severity, and relationship to investigational product.

7.1.3. Severity of Adverse Events

Whenever possible, the severity of all AEs will be graded using the National Cancer Institute Common Terminology Criteria for Adverse Events (NCI-CTCAE), Version 5.0.

The CTCAE quick reference guide can be found at the Cancer Therapy Evaluation Program CTCAE website (CTCAE Website).

For AEs not adequately addressed in the NCI-CTCAE, Version 5.0, the criteria presented in Table 2 should be used.

Table 2: Grading for Adverse Events not Covered in the NCI-CTCAE

| Severity | Description |
|----------------------------|-------------------------------------------------------------------------------------------------------------------------------------------------------------------|
| Grade 1 – Mild | Asymptomatic or mild symptoms; clinical or diagnostic observations only; intervention not indicated |
| Grade 2 – Moderate | Minimal, local, or noninvasive intervention indicated; limited age-appropriate instrumental activities of daily living (ADL) |
| Grade 3 – Severe | Medically significant but not immediately life-threatening; hospitalization or prolongation of hospitalization indicated; disabling; limiting self-care ADL |
| Grade 4 – Life-threatening | Life-threatening consequences; urgent intervention indicated |
| Grade 5 – Fatal | Death |

Abbreviations: ADL, activities of daily living; NCI-CTCAE, National Cancer Institute - Common Terminology Criteria for Adverse Events.

To make sure that there is no confusion or misunderstanding between the terms "serious" and "severe", which are not synonymous, the following note of clarification is provided. The term "severe" is often used to describe the intensity (severity) of a specific event (ie, mild, moderate, or severe); the event itself, however, may be of relatively minor medical significance (eg, severe headache). This is not the same as "serious", which is based on the study participant/event outcome or action criteria associated with events that pose a threat to a participant's life or functioning. Seriousness (not severity) serves as a guide for defining regulatory reporting obligations.

7.1.4. Relationship to Investigational Product

The relationship of an AE to the study drug should be determined by the Investigator according to the following definitions:

- Not Related: Evidence exists that the AE has an etiology other than the study drug
 and/or the temporal relationship of the AE/SAE to the investigational product
 administration makes the relationship unlikely. If an SAE is not considered to be
 related to study drug, then an alternative explanation should be provided.
- Related: A temporal relationship exists between the event onset and the
 administration of the study drug and makes a causal relationship possible or probable.
 It cannot be readily explained by the participant's clinical state or concomitant
 therapies and may appear, with some degree of certainty, to be related based on the
 known therapeutic and pharmacologic actions of the drug. Good clinical judgment
 should be used for determining causal assessment.

7.2. Adverse Event Reporting

7.2.1. General

All AEs will be recorded from the time the study participant signs the ICF/assent form until the Day 91/Day 161 EOS Visit or Early Termination visit, whichever comes first. All AEs must be reported on the AE eCRF via the electronic data capture (EDC) system. The Investigator is responsible for evaluating all AEs, obtaining supporting documents, and ensuring that documentation of the event is complete. Details of each reported AE must include at a minimum severity, relationship to study treatment, duration, and outcome. All (both serious and nonserious) AEs must be followed until they are resolved or stabilized, or until reasonable attempts to determine resolution of the event are exhausted.

Any participant who experiences an AE may be discontinued from study treatment at any time at the discretion of the Investigator. The Sponsor and the CRO Medical Monitor must be notified of the study participant discontinuation.

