4.6. Management of Infusion-Related Reactions (IRR)

Participants will be monitored throughout the infusion and for 60 minutes after completion of study drug infusion for adverse reactions. If an infusion-related reaction (IRR) or hypersensitivity reaction of Grade 3 or higher (Appendix 4) occurs during study drug administration, the infusion should be paused, and the participant should be treated for the

reaction per site standard operating procedures as indicated. The participant will be monitored for resolution of the infusion or hypersensitivity reaction. If the reaction resolves to Grade 1 or less, study drug infusion may be reinitiated. Specific instructions for re-initiation of infusion are provided in the Pharmacy Manual. If the reaction recurs at a level of Grade 3 or higher, study drug administration should be permanently discontinued. Exact times of infusion stop and start must be recorded.

All IRRs will be recorded as an adverse event of special interest (AESI, Section 7.3) or SAE (if serious criterion is met; Section 7.1.2). If the study drug infusion is permanently discontinued, the participant should continue in the study to complete all safety, PK, and PD assessments through Day 161. However, the participant will be ineligible for the OLE study.

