4.8.2. Randomization Method

After all Screening assessments have been completed and the participant is deemed eligible per criteria in Section 3.3.1, participants will be randomized on Day 1 through a central interactive response technology (IRT) system.

Participants will be randomized with a 1:1 ratio to receive treatment with inclacumab or placebo. A stratified permuted block design will be used, with randomization stratified by Baseline HU use (yes; no), number of VOCs (2 to 4; 5 to 10) in the preceding 12 months, and geographic region (North America; rest of world).

The first dose of study drug is to be administered on the same day as randomization (Day 1). No participant may begin treatment with study drug prior to randomization. Any participant identification numbers that are assigned will not be reused even if the participant does not receive treatment.

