8.4.3.6. Safety Analyses

Safety will be assessed through descriptive summaries of adverse events, laboratory test results, and vital signs.

Adverse events will be classified according to the Medical Dictionary for Regulatory Activities (MedDRA). The incidence of TEAEs, defined as events that occur on or after Day 1 of study treatment or the worsening of a pre-existing condition on or after Day 1 of study treatment, will be tabulated by System Organ Class and preferred term. Additional summaries for TEAEs by severity, relationship to study drug, and leading to study drug discontinuation, as well as for AESIs, SAEs, and deaths will be generated.

VOC events will be collected and summarized separately (including ACS, hepatic sequestration, splenic sequestration, and priapism).

Changes in laboratory parameters (hematology, serum chemistry, and coagulation) and vital signs (eg, blood pressure, heart rate, and body temperature) over time will be summarized descriptively.

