3. GENERAL CONSIDERATIONS

3.1. Definitions and Terminology

Study Drug

The term study drug refers to either inclacumab or placebo.

Baseline Value

Baseline is defined as the last available pre-treatment value taken on or before the day of randomization, and will be used for summary of baseline characteristics and change-from-baseline analyses, as appropriate. For ASCQ-Me, baseline is defined as the assessment taken on the day of randomization.

Day 1

Day 1 is the date of randomization.

Study Day

Study Day is defined relative to the date of randomization.

For study assessments or events that occur on or after the date of randomization, study day is calculated as:

Study Day = Event Date - Randomization Date + 1.

For study assessments or events that occur before the date of randomization, study day is calculated as:

Study Day = Event Date – Randomization Date.

Study Visit

Study Visit is the protocol visit as shown in Table 1.

Treatment Day

Treatment Day is defined relative to the date of first dose of study drug.

For study assessments or events that occur on or after the date of first dose, treatment day is calculated as:

Treatment Day = Event Date - First Dose Date + 1.

For study assessments or events that occur before the date of first dose, treatment day is calculated as:

Treatment Day = Event Date – First Dose Date.

Treatment-Emergent Adverse Event

Treatment-emergent adverse events (TEAEs) are defined as adverse events that occur on or after Day 1 of study treatment or the worsening of a preexisting condition on or after Day 1 of study treatment. Note: Given the long half-life of inclacumab, events occurring through end of study will be considered treatment emergent.

Study Completion

Completion of study is specified on the End of Study (EOS) CRF. Participants are considered to have completed the study if (1) the subject completed the study through the Day 91 visit and elected to enroll in the open-label extension study, or (2) the subject did not enroll in the open-label extension study and completed the study through the Day 161 visit.

Treatment Completion

Completion of treatment is specified on the End of Treatment (EOT) CRF and includes all participants who did not permanently discontinue study drug early.

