5.4.3. Clinical Laboratory Assessments

Laboratory abnormalities assessed by the Investigator as clinically significant will be recorded as adverse events.

Descriptive summaries of laboratory parameters (hematology, serum chemistry, and coagulation) at baseline and each evaluation post baseline, as well as changes from baseline over time, will be provided by treatment group. If any of the results are below the limit of quantitation or above the limit of quantitation, then the numerical limit will be used in the descriptive summaries.

Laboratory abnormalities will be graded via the Common Terminology Criteria for Adverse Event (CTCAE). A treatment-emergent laboratory abnormality is any post-baseline laboratory assessment performed on or after initiation of study drug which demonstrates an increase of 1 grade or more from the baseline toxicity value. If the baseline value is missing, any graded abnormality (grade 1 or higher) that occurs following initiation of study drug will be deemed treatment emergent. The number and percentage of participants experiencing treatment-emergent laboratory abnormalities will be summarized by treatment group. Laboratory abnormality shifts from baseline through each evaluation post baseline will be summarized by treatment group.

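### Adverse events that start or worsen on Day 1 before the infusion count as treatment-emergent, and no onset time is required by which to check this

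*Protocol*

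**What the plan says.** **TEAE definition.** SAP 3.1: "Treatment-emergent adverse events (TEAEs) are defined as adverse events that occur on or after Day 1 of study treatment", or that worsen from then on if the condition already existed. SAP 5.4.2 and Protocol 8.4.3.6 use the same rule. SAP 3.1 also states: "Day 1 is the date of randomization".

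**Dosing.** Protocol 4.8.2 and SAP 2.4 place the only dose on the day of randomization.

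**Collection.** Under Protocol 7.2.1, AEs are recorded from signature of the consent or assent form. Its minimum content rule is: "Details of each reported AE must include at a minimum severity, relationship to study treatment, duration, and outcome". Protocol 7.9.1 adds that the investigator determines onset and resolution dates.

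**Infusion times.** Protocol 4.6: "Exact times of infusion stop and start must be recorded".

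**Laboratory abnormalities.** SAP 5.4.3 uses a different anchor. A treatment-emergent abnormality must come from an assessment "performed on or after initiation of study drug".

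**The concern.** A calendar date cannot tell the hours before the infusion from the hours after it. The Day 1 visit includes eligibility review, vital signs, physical examination and a pre-dose blood draw before any drug is given (Protocol 5.3.3, Appendix 1 and Appendix 2), and participants are asked about AEs at each visit. A headache or nausea that starts or worsens during that time is recorded and, by rule, is treatment-emergent.

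TEAE incidence is a named safety endpoint. With a single infusion, Day 1 carries the acute infusion risk. Protocol 7.3 names headache, nausea, vomiting, fatigue and myalgias as possible signs of an infusion-related reaction (IRR), and participants are dosed within 5 days of a resolved crisis, when non-specific symptoms are plausible. Pre-dose events of this kind would add background to both arms and pull between-arm comparisons toward no difference.

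**Working it through.** The plan gives no figure to reproduce, so the check is mainly one of reading the rules together.

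**Step 1. Is the anchor really a date?** Yes. SAP 3.1 equates Day 1 with the randomization date. If Day 1 of study treatment is read instead as the SAP's Treatment Day 1, nothing changes: Treatment Day is also computed from dates, and dosing is on the randomization day.

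**Step 2. Which events does the rule capture?**

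| Event | TEAE now | TEAE if anchored to infusion start |
|---|---|---|
| Began before Day 1, did not worsen | No | No |
| Began before Day 1, worsened on Day 1 before infusion | Yes | No |
| Began on Day 1 before infusion | Yes | No |
| Began or worsened during or after infusion | Yes | Yes |

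Only the second and third rows are misclassified.

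**Step 3. Can those rows be found from the required data?** Protocol 7.2.1 asks for severity, relationship, duration and outcome, and 7.9.1 asks for dates. No section requires an AE clock time. Infusion times should exist: besides the rule in 4.6, which stands in the IRR section, Protocol 8.4.2 plans to summarize infusion time, and Appendix 2 times samples from the end of infusion. The comparison therefore lacks only the AE side.

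**Step 4. Which tables are affected?** Of the tables listed in SAP 5.4.2, mainly all TEAEs, maximum severity, and the preferred-term counts within them. The related-event and IRR tables are better protected, because both depend on the investigator's view of timing.

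**Step 5. How large could it be?** Neither a pre-infusion AE rate nor TEAE risks are given, so all inputs here are assumptions. Let p be the true risk of a TEAE, and m the share of participants, equal in both arms, with a misclassified pre-infusion event that is independent of the true events.

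- Observed risk = 1 − (1 − p)(1 − m)
- Observed risk difference = true difference × (1 − m)

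About 0.26 × 280 = 72.8, or 73 participants, were randomized. So m of 2%, 5% and 10% means about 1.5, 3.6 and 7.3 participants.

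| Assumed true risks | True ratio | m = 2% | m = 5% | m = 10% |
|---|---|---|---|---|
| 60% vs 50% | 1.20 | 60.8/51.0 = 1.19 | 62.0/52.5 = 1.18 | 64.0/55.0 = 1.16 |
| 30% vs 20% | 1.50 | 31.4/21.6 = 1.45 | 33.5/24.0 = 1.40 | 37.0/28.0 = 1.32 |
| 10% vs 5% | 2.00 | 11.8/6.9 = 1.71 | 14.5/9.75 = 1.49 | 19.0/14.5 = 1.31 |

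In each of the first two rows the risk difference falls from 10.0 points to 9.8, 9.5 and 9.0. In the third it falls from 5.0 to 4.9, 4.75 and 4.5.

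**The case against.** The strongest reply is that little of clinical importance is lost, and much of it stands.

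- **Residual crisis symptoms are mostly excluded.** A reader might infer that any symptom present before the infusion becomes a TEAE. The documents do not support that: a pre-existing condition counts only if it worsens on or after Day 1. VOC events themselves are not reported as AEs (Protocol 7.6).
- **Reactions are identified separately.** A reader might infer that infusion reactions cannot be told apart from background. Protocol 4.6 and 7.3 flag every IRR as an AE of special interest, SAP 5.4.2 gives these a summary and a listing, and Protocol 7.1.4 bases relatedness on timing relative to administration. What remains is that this separation rests on investigator judgement and cannot be verified against infusion times unless an onset time exists.
- **The eCRF may collect onset time.** The list in 7.2.1 is a minimum, and the eCRF is not among the documents. If it does collect time, the definition can be applied with fewer queries.
- **Large dilution figures are contrived.** For one infusion-type symptom at 10% versus 2%, m = 10% gives 0.190/0.118 = 1.6 in place of 5.0. That needs a tenth of participants to have that same symptom start or worsen on Day 1 before dosing. The risk difference moves only from 8.0 to 7.2 points, and 2% of about 36 per arm is 0.7 of a participant. Safety analysis is descriptive, and no risk ratio is planned.
- **The date rule is inclusive.** It misses no post-infusion event. That is a real merit for detection, but it does not make the between-arm comparison conservative.

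**Conclusion.** The point holds in a limited form. The TEAE definition counts AEs with onset or worsening on Day 1 before the infusion, and the documents require no onset time that would let anyone check this against the infusion record. The SAP gives no reason for anchoring laboratory abnormalities to study-drug initiation and TEAEs to a date.

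The expected effect is a small addition of background to both arms. Because the trial is blinded and the events precede dosing, neither arm is favoured in expectation, although actual counts in arms of about 36 can differ by chance. The true size is unknown. The ratios above illustrate direction and rest on an assumed m of 2% to 10%, assumed TEAE risks, equal m in both arms, and independence. This is a minor defect of definition, not a threat to the safety conclusions.

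**What to change.** In SAP 3.1 and 5.4.2, define a TEAE as an AE with onset or worsening at or after the start of the study drug infusion, matching the anchor in SAP 5.4.3. SAP section 2 says that the SAP supersedes the protocol where they differ, so Protocol 8.4.3.6 need not be amended.

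Before database lock, classify AEs dated Day 1 as before, during or after the infusion, using onset time where the eCRF has it and a site query where it does not. If timing stays unknown, count the event as treatment-emergent, which keeps the present inclusive default.

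A new eCRF field for prospective use would add little, since the study was discontinued before full enrolment and each participant has one dose on Day 1.

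The cost is a change to one definition and a short query limited to Day 1 events. The downside is that some events will remain unclassified by timing and will be counted as they are now.

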7.2.2. Diagnosis Versus Signs and Symptoms

If known, a diagnosis should be recorded on the eCRF rather than individual signs and symptoms (eg, record only liver failure or hepatitis rather than jaundice, asterixis, and elevated transaminases). However, if a constellation of signs and/or symptoms cannot be medically characterized as a single diagnosis or syndrome at the time of reporting, each individual event

should be recorded separately on the eCRF. If a diagnosis is subsequently established, it should be reported as follow-up information.

7.2.3. Abnormal Laboratory Values

Clinically significant laboratory abnormalities will be recorded in the AE eCRF (eg, abnormalities that have clinical sequelae, more frequent follow-up assessments, or further diagnostic investigation). If the clinically significant laboratory abnormality is a sign of a disease or syndrome (eg, alkaline phosphatase and bilirubin 5 × upper limit of normal [ULN] associated with cholecystitis), only the diagnosis (eg, cholecystitis) needs to be recorded in the eCRF.

If the clinically significant laboratory abnormality is not a sign of a disease or syndrome, the abnormality itself should be recorded on the eCRF. If the laboratory abnormality can be characterized by a precise clinical term, the clinical term should be recorded. For example, an elevated serum potassium level of 7.0 mEq/L should be recorded as "hyperkalemia".

Observations of the same clinically significant laboratory abnormality from visit to visit should not be repeatedly recorded on the AE eCRF, unless their severity, seriousness, or etiology changes.

7.3. Adverse Events of Special Interest, Serious Adverse Events, Serious Adverse Drug Reactions, and Requirements for Immediate Reporting

Any biologic agent administered IV may have the potential to cause infusion-related reactions (IRR; see Investigator's Brochure). In this study, IRRs should be reported as adverse events of special interest (AESI). Signs or symptoms of IRRs may include chills/rigors, myalgias, headache, rash, fatigue, nausea, vomiting, dyspnea, and/or hypotension. Shock may occur during or shortly after infusion and usually occurs during and/or up to 24 hours after the first infusion.

All AESIs or SAEs, regardless of causal attribution, must be reported by the Investigator or designee or site personnel within 24 hours of AESI or SAE awareness. The AESI or SAE will be reported by completing the SAE eCRF. AESIs will be recorded on the SAE eCRF within 24 hours of the site's awareness of them, even if they do not meet criteria for an SAE.

The Sponsor or designee may request additional source documentation pertaining to the AESI or SAE from the investigational site. Follow-up reports must be submitted within 24 hours of awareness, and participant identifier information (eg, name, medical record number) must be redacted in the hospital discharge summaries, autopsy reports, and/or death certificates.

Follow-up AESI or SAE information must be submitted within 24 hours of awareness as additional information becomes available. All AESI or SAEs regardless of causal attribution must be followed to resolution or stabilization, or until reasonable attempts to determine resolution of the AESI or SAE are performed.

